We hypothesize that nifedipine treatment of hypertensive parturient women will be more effective than labetalol or methyldopa in controlling high blood pressure (defined as 120-150mmHg systolic and 70-100 mm Hg diastolic) within 6h. Brown et al found that 83% of pregnant women with severe hypertension treated with nifedipine had successful lowering of blood pressure 110 to 169/80 to 109 mm Hg by 90 minutes without an adverse outcome.¹⁷ Our trial will enroll sicker patients and our goal is lower and lasting control. Based on the (scant) available literature, we hypothesize that nifedipine will control 75% of high blood

pressure within 6 hours and labetalol and methyldopa will be able to control 62.5% and 62.5%, respectively. As the subjects in the nifedipine study group will serve as a comparison group for both the labetalol and methyldopa regimens, the comparison of labetalol and nifedipine requires a sample size of 261 in each study group given a two tailed test, $\alpha=0.05$ and $1-\beta=80\%$, and a simple Bonferroni correction. Using the same statistical assumptions, with a nifedipine sample size of 261, the methyldopa study group requires 261 subjects. In order to account for loss to follow-up, we will enroll 894 women total (nifedipine: 298 women; labetalol: 298 women; methyldopa: 298 women).

Proposed Analyses

After the data are entered, they will be converted into an SPSS for Windows data file, reviewed for logical inconsistencies, cleaned, and analyzed.

For each of the regimens, we will calculate the following statistics:

- % of women who reach the target (defined as 120-150mmHg systolic and 70-100 mmHg mm Hg diastolic) within 6h without any specified adverse outcome (see above)
- % of women who reach the target (defined as 120-150mmHg systolic and 70-100 mmHg mm Hg diastolic) within 3h without any specified adverse outcome (see above)
- % of women who experience an adverse outcome. Adverse outcomes include hypotension (systolic blood pressure, <120 mm Hg and/or diastolic blood pressure <70 mm Hg and fetal compromise), caesarean section for fetal distress, severe headache or eclampsia.

- % of women who reach an intermediate target (defined as 120-159 mmHg systolic and 70-104 mmHg diastolic) within 6 hours without an adverse outcome.
- % of time systolic and diastolic blood pressure in target range

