Logistic, Poisson and negative binomial regression models will be used as appropriate to estimate effect size (difference in attainment of treatment goal rates) with 95% confidence intervals. Adjustments in 95% confidence intervals will be made for important confounding variables and covariates including: mean arterial pressure at the initiation of therapy; heart rate at the initiation of therapy; mode of admission; evidence of abnormal laboratory results; history of chronic hypertension; diabetes (gestational or medicated); gestational age; and birth weight percentile. The primary analysis will be done according to intention to treat. If indicated, a secondary, per protocol analyses will be performed. Similar regression models will be used to compare the two study groups with respect to other important (secondary) variables.

TRIAL MANAGEMENT AND OVERSIGHT ARRANGEMENTS

Trial Sponsorship

University of British Columbia

Trial Management

The study team at Gynuity Health Projects and GMC Nagpur will develop the study materials in line with the protocol. The day-to-day running of the study will be the responsibility of the Gynuity-Nagpur team who have extensive experience in conducting high quality studies in low resource settings. Prior to the start of the trial, the required local and national ethical approvals will be obtained by the Gynuity-Nagpur team who will also develop the trial documentation including data collection forms, patient information leaflet, consent form and trial standard

operating procedures (SOPs). Randomisation will be by means of random numbers centrally generated in distinct blocks. Randomisation and packaging will be by Gynuity Health Projects by staff not otherwise involved in the study. Gynuity-Nagpur will also train the local research team, manage routine trial logistics, establish a standard data entry system for trial data, supervise data entry, conduct quality checks on data entry system, and establish a backup system for trial database and relevant electronic files.

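### The sample size is built on a Bonferroni correction for two comparisons, but the analysis section specifies 95% intervals and does not carry the correction forward

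*Protocol*

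**What the plan says.** Protocol, Sample Size Calculation, assumes control of blood pressure within 6 hours in 75% of women on nifedipine and 62.5% on each of labetalol and methyldopa. Nifedipine is the shared comparator: "As the subjects in the nifedipine study group will serve as a comparison group for both the labetalol and methyldopa regimens". The calculation is two-tailed with alpha 0.05 and 80% power "and a simple Bonferroni correction". The result is that "the comparison of labetalol and nifedipine requires a sample size of 261 in each study group", with the same number for methyldopa. Enrolment is set at 298 per arm, 894 in total, to allow for loss to follow-up. The divisor of the correction is not stated.

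Protocol, Proposed Analyses, says that logistic, Poisson and negative binomial models "will be used as appropriate to estimate effect size (difference in attainment of treatment goal rates) with 95% confidence intervals". The next sentence provides for adjusting these 95% intervals for a list of confounders and covariates. The section does not mention multiplicity, a significance level for the final primary test, or which pairs of arms are primary. It closes by saying that similar models will be used to "compare the two study groups with respect to other important (secondary) variables", although the trial has three arms.

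**The concern.** The two sections work at different levels. One pays, in patients, for a stricter standard per comparison. The other fixes the ordinary 95% level for the effect estimates and mentions only covariates as a reason to adjust them. An analyst following Proposed Analyses alone would produce two 95% intervals for the nifedipine contrasts, and readers would naturally take an interval that excludes no difference as a positive primary result. That is a looser standard than the design intended. The count of two groups in the same paragraph adds to the impression that the section was not aligned with a three-arm, two-comparison design.

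At stake is the trial-wide false-positive rate. There is also a band of results in which a 95% interval would exclude no difference while the Bonferroni test would not reject.

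**Working it through.** **Inputs.** From Sample Size Calculation: p1 = 0.75, p2 = 0.625, difference d = 0.125, two-sided, power 80% (z = 0.842), 261 evaluable and 298 enrolled per arm, two comparisons sharing nifedipine. From Proposed Analyses: 95% intervals.

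**1. Reproduce the 261.** Two proportions, pooled variance under the null, no continuity correction:

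n = [z(1−α/2)·√(2·p̄·(1−p̄)) + 0.842·√(p1(1−p1) + p2(1−p2))]² / d²

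Here p̄ = 0.6875, so the first root is √0.4297 = 0.6555. The second is √(0.1875 + 0.2344) = 0.6495.

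- α = 0.025 (z = 2.241): (1.469 + 0.547)² / 0.015625 = 260.1, so **261**, as stated.
- α = 0.05 (z = 1.960): (1.285 + 0.547)² / 0.015625 = 214.7, so 215.
- α = 0.05/3: 286.5, so 287.

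With a continuity correction the three values are 276, 231 and 303. Only two comparisons at 0.025 each, without continuity correction, gives 261. The correction accounts for 261 − 215 = 46 evaluable women per arm, or 138 in all.

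**2. Family-wise error if 95% intervals decide.** Suppose all three success rates are equal. With equal arms, the two contrasts share the nifedipine variance, which is half the variance of each contrast, so the test statistics have correlation 0.5. For a bivariate normal pair, the error is 1 − P(|Z1| < c and |Z2| < c).

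| Level per comparison | c | Family-wise error, correlation 0.5 | If independent | Bonferroni bound |
|---|---|---|---|---|
| 0.05 (95% interval) | 1.960 | **9.1%** | 9.75% | 10% |
| 0.025 (97.5% interval) | 2.241 | **4.6%** | 4.9% | 5% |

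Binomial simulation (400,000 runs; 261 and 298 per arm; common rates 62.5% and 75%) gave 8.8% to 9.4% for the first row and 4.6% to 4.7% for the second.

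**3. Where the two standards disagree.** At 261 per arm, the pooled standard error is √(0.4297/261) = 0.0406. The 5% threshold is 1.960 × 0.0406 = 8.0 points and the 2.5% threshold is 2.241 × 0.0406 = 9.1 points. Observed differences of about 8.0 to 9.1 points would be positive on one standard and not on the other.

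**4. Cost of aligning them.** The ratio of interval widths is 2.241/1.960 = 1.14. Power per comparison at 0.025 is 80.2% with 261 per arm and 85.5% with 298.

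**The case against.** The strongest reply is that Proposed Analyses uses the 95% intervals to estimate effect size. It does not say that an interval excluding no difference is a positive result. The only testing level in the protocol is the Bonferroni-corrected one, and no passage withdraws it. Reporting 95% intervals is compatible with testing each comparison at 0.025, and a statistical analysis plan that is not shown may say exactly that. This stands, and it makes the 9% conditional. It does not remove the mismatch: the protocol does more than stay silent, because it writes in an interval level that differs from the level it powered.

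Two further replies stand in part. The primary contrasts can be inferred from the hypothesis that nifedipine is better than each of the other drugs, so naming them is a clarification. The count of two groups appears only in the sentence on secondary variables, so it is a slip that says nothing direct about the primary error rate.

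One could also note that, with unadjusted intervals, the chance of falsely favouring nifedipine at least once is only 4.5%. But the plan is two-tailed, so its 5% covers errors in both directions.

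Some stronger readings are tempting. A reader might infer that all three pairs will be tested and the error rate is higher still; labetalol v methyldopa is neither hypothesised nor powered. A reader might also infer that the primary yes/no outcome will be fitted by a Poisson model with model-based errors and lose most of its power. The phrase allowing each model where appropriate does not assign Poisson to that outcome, and the protocol lists count outcomes (blood pressure readings above or below range) for which it would be natural. Intervals that wide would also make the tests conservative, so this reading cannot hold together with a 9% error rate. How a rate difference is obtained from a logistic model is detail for the analysis plan.

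**Conclusion.** The point holds as an inconsistency within the protocol. The sample size corresponds to two comparisons at two-sided 0.025, while the analysis section specifies 95% intervals without carrying the correction over. If those intervals decide the two nifedipine comparisons, the family-wise false-positive rate is about 9% instead of at most 5%; at 0.025 each it is 4.6%.

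A reader might infer that the trial's false-positive rate is 9% as planned. The document does not support that, because it gives no such decision rule and keeps the Bonferroni statement.

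The figures assume equal arms, all three success rates equal, and the large-sample normal approximation, which the simulation supports. They leave out the interim look. Its boundary of 0.001 could add at most 0.1 percentage points if applied as one three-group test, or 2 × 0.1 = 0.2 points if applied to each comparison. This is a clarification that should be made before the final analysis. It does not undermine the design or the number of patients.

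**What to change.** In Proposed Analyses:

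- Name nifedipine v labetalol and nifedipine v methyldopa as the two primary comparisons.
- State that each is tested at two-sided 0.025 and reported with a 97.5% confidence interval.
- Label labetalol v methyldopa as secondary.
- Correct the count of study groups from two to three.

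In Sample Size Calculation, it would help to state the divisor: two comparisons, 0.025 each.

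The cost is primary intervals about 14% wider. No extra patients are needed, since 261 per arm already gives the stated 80% power at this level. If a statistical analysis plan already sets 0.025 per comparison, the change only brings the protocol into line with it.

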After receiving written consent from the participant, the next consecutive, sequentially numbered opaque envelope will be withdrawn from the study dispenser. A card indicating the woman's treatment assignment will be included in the envelope. The card designating the treatment group will be attached to Form 1. The group assignments will be randomised independently using a computerised pseudo-random number generator; the randomisation will be stratified by centre.

Treatment Allocation

Sequence generation will be through a random sequence allocation computer programme. The provider will not be blinded to the treatment allocation.

The clinicians in both centres will undergo training in the use of the three treatment regimens. Guidelines for the management of treatment will be drawn up in collaboration with those in the centres so as to prevent operator bias through protocol deviations. The outcome data will be collected prospectively by study staff in order to ensure that the data collection is as complete as possible. Identical data tables will be used for the data monitoring committee and the final report in order to prevent reporting bias.

Study Interventions

Women in **Group A** will receive an initial dose of oral nifedipine 10mg. If blood pressure exceeds 155mmHg systolic OR 105 mmHg diastolic after 1h, an additional 10mg dose can be provided each hour for two additional doses (30 mg total).

Women in **Group B** will receive an initial dose of oral labetalol 200mg. If blood pressure exceeds 155mmHg systolic OR 105 mmHg diastolic after 1h, an additional 200mg dose can be provided each hour for two additional doses (600 mg total).

Women in **Group C** will receive an initial dose of oral methyldopa 1000mg. No additional escalation in dose in the first 6 hours will be given.

A range is provided in the threshold for dose escalation to permit input from clinical judgment. The maximum doses are based on the upper limits of effective dose range for each medication over 24 hours: nifedipine – 120mg; labetalol 2400mg; methyldopa – 2000 mg. The treatment goal (defined as 120-150 mmHg systolic and 70-100 mmHg diastolic) has been chosen based on NICE criteria. The relatively wide range between entry criteria and treatment goal should offer the best opportunity to discover differences in clinical response.

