If the treatment goal (defined as 120-150 mmHg systolic and 70-100 mmHg diastolic) is achieved at 6h, treatment will be continued up to 24 hours postpartum unless deemed clinically unnecessary after delivery. The ongoing dose will be determined by the clinical care team based initially on the dose required over the first 6 hours and the clinical response after 6 hours. If the treatment goal is not achieved at 6h, women will receive the standard of care treatment for this indication. Women in the nifedipine group who do not achieve the treatment goal will continue to receive nifedipine 10mg. Women in the labetalol group who do not achieve the treatment goal will receive labetalol 200mg and women in the methyldopa group will receive either nifedipine 10mg or labetalol 200mg according to the treating physician's preference. In all cases, blood pressure monitoring will occur regularly as per standard hospital practice. During the treatment of a patient, the clinical team can determine that the study protocol should be discontinued due to 1) ineffective response resulting in clinically unsafe blood pressures or 2) significant side effects. Indications for stopping the treatment protocol will be recorded and study endpoints will be collected. Prior to and after enrollment in the trial, women in all groups should be treated with magnesium sulfate if clinically indicated and as per the standard treatment protocols at each facility. The use of magnesium sulfate and nifedipine together does not increase

the risk of serious magnesium-related side effects including hypotension (Magee et al 2005).

After the administration of the drugs, blood pressure and pulse will be recorded every 20 minutes. Blood pressure will be measured with an automatic digital blood pressure cuff. Oxygen saturation will be measured and recorded every 2h until 6h. The Glasgow Coma Scale will be administered by a research clinician at 0, 2, and 6h. AST (liver enzyme test), platelet count and creatinine will be performed at the start of antihypertensive treatment (0h), and 6 hours. Maternal side effects will be assessed at 0h, 2h, and 6h. Fetal heart rate will be recorded at 0 and 6h.

Study Outcomes

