A post-study interview with the woman will be conducted once she is stable and prior to her discharge from the study hospital. Women will be interviewed and asked about their experience with pain and side effects. Women will be asked to rate their overall experience on a categorical five-point scale from 'very unsatisfied' to 'very satisfied'. Instruments will be informed by prior research on the acceptability of new medical technologies for delivery of magnesium sulphate among Indian women.

Data will be collected throughout the woman's admission, with data collection stopping postnatally at time of discharge or maternal death. No further follow-up is planned.

Pilot Study

Given the uncertainty of the effect of each of these drugs on this population, we will conduct a pilot study (n=30) prior to the start of the trial. The purpose of this pilot is to test the feasibility of the study protocol as designed. Women will be allocated serially to one of three oral antihypertensive regimens regimens: methyldopa (n=10), labetalol (n=10), or nifedipine (n=10).

The primary aim of the pilot study is to assess the three proposed drug regimens and, potentially, reveal the need for a lower dose. Methyldopa may not be effective for acute control of severe hypertension. However, in many settings where labetalol or nifedipine are not available, methyldopa is the oral drug of choice. Given our concerns about the slow onset and general lack of potency of

methyldopa, we are conducting a pilot study to assess whether it is appropriate to include it in the trial. If the success rate in any of the three arms is less than 30% (3/10) then the investigators will assess whether to include the regimen in the RCT. The secondary aims of the pilot are to (1) assess adverse outcomes and necessity for additional antihypertensive treatment among women in the three study arms; and (2) to evaluate data collection tools (including use of the Glasgow Coma Scale and assessments of women's attitudes post-treatment) in the subsequent trial.

Required ethical approvals for the pilot study have been obtained from Government Medical College Nagpur and the University of British Columbia.

Study Assessment and Data Collection Forms

Form 1: Screening Form. This form will determine a woman's eligibility for enrollment in the study. The form will also document basic demographic characteristics and obstetrical history.

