Form 2: Monitoring Form (0-6h): This form will record the actual (rather than protocol) time for the administration of each dose. Assessment of blood pressure and pulse will be recorded every 20 minutes. Oxygen saturation will be measured and recorded every 2h. Maternal side effects including headache pain, nausea and vomiting, visual disturbances, urine output, right upper quadrant and epigastric pain will be assessed and recorded at the start of antihypertensive treatment (0h), 2h, 4h, and 6h. The Glasgow Coma Scale will be administered at 0, 2, and 6h by the attending research clinician. Although not specifically designed for this use, it is the best tool for assessment in this clinical environment. The utility of this tool for this trial will be assessed during the pilot study.

Form 3: Laboratory Results: This form will record the results of all laboratory tests. Liver enzyme tests, creatinine and platelet counts will be performed at 0h and 6 hours.

Form 4: Maternal Outcomes: The clinician will also note the final outcome of the woman including any interventions undertaken during labor and delivery. This information may be abstracted from patient charts if available.

Form 5: Neonatal Outcomes: The clinician will also note the final outcome of the baby including any interventions undertaken during labor and delivery. This information may be abstracted from patient charts if available.

Form 6: Exit Interview: The interview with the woman will be conducted once she is stable and prior to her discharge from the study hospital. This form will record her attitudes and opinions regarding the mode of treatment including experience with pain and side effects.

Form 7: Case Summary. Clinicians will complete a case summary form for each woman after she is discharged from the study. The form will summarize data recorded on other forms and confirm the number of doses administered, adverse events, and treatment discontinuation.

STATISTICS AND DATA ANALYSIS

Sample Size Calculation

The primary outcome will be control of high blood pressure (defined as 120-150mmHg systolic and 70-100 mm Hg diastolic) within 6h.

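### The adjustment list includes birth weight percentile, which is known only after delivery; a complete-case adjusted analysis of the 6h effect can therefore drop randomised women, contrary to intention to treat

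*Protocol*

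**What the plan says.** In the protocol, the Proposed Analyses section plans logistic, Poisson or negative binomial regression for the difference in attainment of the treatment goal. It states: "Adjustments in 95% confidence intervals will be made for important confounding variables and covariates including: mean arterial pressure at the initiation of therapy". The list goes on with "heart rate at the initiation of therapy; mode of admission; evidence of abnormal laboratory results; history of chronic hypertension" and closes with "diabetes (gestational or medicated); gestational age; and birth weight percentile". The same paragraph says that the primary analysis follows intention to treat.

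Four other places bear on this list:

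- **Outcome timing.** The Sample Size Calculation section sets the primary outcome as blood pressure control within 6h.
- **End of data collection.** The Study Outcomes section describes collection during the admission, "with data collection stopping postnatally at time of discharge or maternal death", and plans no follow-up beyond that. The interval from enrolment to delivery is itself an outcome.
- **Laboratory tests.** Under Study Interventions the tests "will be performed at the start of antihypertensive treatment (0h), and 6 hours", and the entry for Form 3 repeats this: "Liver enzyme tests, creatinine and platelet counts will be performed at 0h and 6 hours".
- **Randomisation.** The Randomisation section says that "the randomisation will be stratified by centre". There are two centres.

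**The concern.** A covariate in a randomised comparison should be fixed before treatment starts. Birth weight percentile is not: it comes into being at delivery, while the treatment comparison concerns the first 6h. Two consequences follow.

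First, the estimate is conditioned on something measured after randomisation, which can distort it if treatment affects that variable.

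Second, standard regression software drops any woman who lacks a covariate value. Women enter from 28 weeks, and collection ends at discharge. A woman who goes home undelivered would have a full 6h outcome and no birth weight, and would leave an analysis that is meant to include everyone randomised.

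The laboratory item raises a lesser version of the first problem, because a 6h result could reflect the drug. Centre is the one factor built into the randomisation, yet it does not appear among the eight covariates named.

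**Working it through.** **1. Timing of each named covariate.** Mean arterial pressure and heart rate are expressly tied to the start of therapy. Mode of admission, chronic hypertension and diabetes are history or entry items. Gestational age carries no time label, but it is an entry criterion. The laboratory item carries no time label and is measured both at 0h and at 6h. Birth weight percentile is the only item that cannot be read as a baseline value.

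**2. The protocol's own sample size.** Inputs from the Sample Size Calculation section: p1 = 0.75, p2 = 0.625, two-sided α = 0.05 with a Bonferroni correction over two comparisons (0.025, z = 2.2414), and power 80% (z = 0.8416). The mean proportion is 0.6875.

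n = [2.2414·√(2·0.6875·0.3125) + 0.8416·√(0.75·0.25 + 0.625·0.375)]² / 0.125²
= (1.4693 + 0.5466)² / 0.015625 ≈ 260.1, so 261 per arm.

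This matches the stated 261. Enrolment is 894/3 = 298 per arm, an implied loss allowance of 1 − 261/298 = 12.4%.

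**3. Power if women without a birth weight are dropped.** Power = Φ[(0.125·√n − 1.4693)/0.6495]. The share missing is an assumption, as the protocol gives none. Success rates are taken to be the same in women with and without a value, and no gain in precision from covariates is counted.

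| Assumed share missing | n per arm from 298 | Power | n per arm from 261 | Power |
|---|---|---|---|---|
| 0% | 298 | 85.5% | 261 | 80.2% |
| 5% | 283 | 83.5% | 248 | 77.9% |
| 10% | 268 | 81.3% | 235 | 75.4% |
| 15% | 253 | 78.8% | 222 | 72.7% |
| 20% | 238 | 76.1% | 209 | 69.8% |

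The left-hand pair applies if birth weight is the only cause of loss. The right-hand pair applies if the 12.4% allowance has already been spent on other losses. Starting from 298, a loss of 12.4% brings the arm back to 261 and 80.2%, so power goes below 80% just beyond that point.

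**4. Omitting centre.** A simulation used two equal centres, 298 per arm, arms exactly balanced within each centre, 20,000 replicates and a nominal type I error of 0.025. The simulation error is √(0.025·0.975/20,000) ≈ 0.001.

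| Difference in success rate between centres | Type I error, centre left out |
|---|---|
| 0 points | 0.025 |
| 10 points | 0.026 |
| 20 points | 0.023 |
| 40 points | 0.014 |

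The first two are nominal within simulation error. The test becomes conservative only as the centres diverge widely.

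**5. A 6h laboratory covariate, by illustration.** Assume that 30% of the comparator arm have an abnormal result, that an abnormal result lowers success by 25 points, and that the direct effect of treatment is 10 points. If treatment cuts abnormal results by 20%, the total effect is 10 + 25·0.30·0.20 = 11.5 points. If it cuts them by 50%, the total effect is 10 + 25·0.30·0.50 = 13.75 points. Adjusting for the 6h result returns about 10 in both cases. If treatment does not change the result, there is no bias.

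**The case against.** The case against a wide reading is strong, and most of it stands.

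- **The adjusted model may not be primary.** A reader might infer that women are lost from the primary analysis. The protocol does not say so. It lists simple percentages per regimen first, and the 261 reproduces as an unadjusted comparison of two proportions. Dropping women also presumes complete-case handling, and the protocol names no missing-data method. That detail may properly sit in the analysis plan.
- **Missing birth weights may be few.** Treatment may run to 24 hours postpartum, and collection is described as stopping postnatally. Both suggest that delivery was mostly expected in the same admission. No rate is given.
- **Power need not fall below 80%.** That inference follows only if the loss allowance is already used up, or if more than about 12.4% of the 298 are lost.
- **Bias through growth is weakly supported.** The Risks to the Participants section says, of beta-blockers, that the short exposure should not measurably affect growth. The percentile may largely reflect growth before entry.
- **The laboratory item has a natural baseline reading.** It stands among confounders, next to two items fixed at the start of therapy. A reader might infer that 6h values will be used, but the text leaves this open.
- **Centre is not excluded.** The list is open-ended, and stratification balances the arms whether or not centre is modelled. The inference that leaving it out wastes the stratification or seriously misstates the standard error is not borne out by the simulation.

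One thing is not answered. The protocol did not leave the covariates to a later document: it says that adjustment will be made for birth weight percentile. Imputing the value would keep the women in the model, but the model would still adjust for something measured after randomisation.

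**Conclusion.** The point holds for birth weight percentile. As written, the plan adjusts a 6h treatment effect for a variable that does not exist until delivery. In a complete-case model this can remove randomised women with a complete outcome, which conflicts with the stated intention-to-treat analysis.

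The size is uncertain, because the share missing is unknown and the role of the adjusted model is not stated. The cost in power runs from slight (85.5% to 83.5% with 5% missing from 298 per arm) to moderate (80.2% to 75.4% with 10% missing from 261). Bias through growth cannot be sized from the protocol and is probably small.

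The laboratory time point is an ambiguity to close. Naming centre is good practice; leaving it out is not a serious error. The change should be made because the fault is clear and the correction is cheap, not because large harm has been shown.

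**What to change.** In the Proposed Analyses section:

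1. Delete birth weight percentile from the adjustment list. Keep it, if wanted, for description or exploration of neonatal outcomes.
2. Specify the laboratory item as results at 0h.
3. Specify gestational age as that at enrolment. This is a clarification only.
4. Add centre (two levels) as a covariate.

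These are wording changes. They need no new data and leave 261 evaluable and 298 enrolled per arm (894 in total) as they are. No woman with a 6h outcome would then be dropped for want of a birth weight.
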